#### Overview of open label dose-escalation study goals and methodology

We conducted a Phase IIa, open label dose-escalation tolerability study (NCT02818777) in 13 PD patients at the University of Colorado between October 2016 and June 2017, using Epidiolex®. The primary outcome was safety and tolerability, measured by adverse events, changes in examinations, labs, EKGs and percentage of participants that discontinued study drug due to intolerability. The major secondary outcome measure was change in the total of two items on rest tremor in the MDS-UPDRS, and others were measures of most motor and non-motor symptoms that occur in PD. Participants had a screening visit, a baseline visit within the next three weeks, a final dose assessment visit when they have been on the maximal tolerated or the targeted study dose for 10-15 days, and a safety visit 2 weeks later. From the baseline visit, qualified participants took Epidiolex® in a 100 mg per mL sesame oil-based solution orally twice daily. Since somnolence was a reported adverse effect in the pediatric epilepsy population, and Epidiolex® had not been used in persons over age 50, we elected to be cautious and instructed participants not to drive while on study drug.

CBD was started at 5 mg/kg/day and the dose could be increased or decreased by up to 2.5 to 5 mg/kg/day until the study participants reached a maximum targeted dose (20-25 mg/kg/day) or experienced intolerable adverse events (AEs), in which case the dose would be dropped to the last

tolerated dose. Tolerability was assessed via collection of AEs during administration of the standardized phone script by study staff on the third or fifth day of each dose, and the participants were instructed whether or not to change the dose at the end of phone call. Participants filled out home diaries to increase and monitor compliance.

Participants were called at the end of each dose level. During phone calls participants were monitored for AEs, especially excessive daytime sleepiness, symptoms of hepatotoxicity, as well as changes in medical history and concomitant medications. Participants were also called three days after stopping CBD to check for signs of withdrawal. The primary outcome was safety and tolerability of CBD and the secondary and exploratory outcomes examined the effect of CBD on severity and duration of tremor and other conditions that occur in PD.

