The study is a randomized, placebo controlled, double-blind parallel design with two treatment arms, each of approximately 2-3 weeks duration. In the 2-3 week treatment phase participants will start study drug and titrate up to the maximum tolerated or targeted dose (2.5 mg/kg/day of CBD). Each participant will have a screening visit, baseline visit within four weeks, 2 dose assessment visits (1.25 mg/kg/day and 2.5 mg/kg/day), and a safety visit (5 visits total). Participants will be evaluated at each dose level for monitoring adverse events, as well as changes in medical history and concomitant medications. Further, in case CBD alters the reliability of self - report, repeated measures will be taken on the third to fifth day at each dose during the clinic visits or at home. The assessments include the assessment of tolerability and symptoms of hepatotoxicity, SCOPA-sleep, Anxiety short form, Depression short form, Emotional and behavioral dyscontrol short form, and EQ-5D-5L. Participants are called 3 and 7 days after stopping the study drug to check for signs of withdrawal. At dose assessment visits, urinary CBD and metabolites will be tested. To maximize compliance the coordinator calls the participant to remind them the next day's clinical visit. To increase compliance with taking study drug, participants will be asked to fill out a diary at home. The diary will be a record of the date and time participants take study drug, dose of the study drug, and adverse and beneficial events. Study drug is dispensed at the baseline visit. Participants will measure their tremor using Tremor GUI MATLAB twice a day (two hours after breakfast dose and two hours after dinner dose) for two consecutive days after screening visit, three consecutive days prior to baseline and each dose assessment visit, as well as during the clinic visits. To evaluate the possible somnolence effect of CBD, participants will be evaluated their alertness before and three hours after they take the study drug at baseline visit.

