## Dose escalation strategy:

Study product (CBD or placebo) will be started at 1.25 mg/kg/day of CBD (once a day) for four days and then increase to 2.5 mg/kg/day of CBD (twice a day) for 10 (+4) days. Tolerability will be assessed at each dose during each clinic visit. Subjects may take a reduced dose for the duration of the study according to the investigator's medical judgement.

Regarding possible drug interactions, study pharmacists will be provided the calculated dose based on body weight, the list of the subject's medications, and additional relevant clinical information. The final study drug dose will be that recommended by the study pharmacists.

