Visit 3 (3-4 days, 1.25 mg/kg/day) and Visit 4 (14 (+4) days, 2.5 mg/kg/day), dose assessment visits: On the morning of the visits, participants will collect their urine and bring it to the visits. Study coordinator will collect and store the urine cups in a -80°C freezer until shipment for urinary CBD and metabolites test. Concomitant medications, change in medical history, vital signs, orthostatic blood pressures, complete physical exam, detailed neurological exam, MDS-UPDRS, UDysRS, H&Y rating, tremor constancy and amplitude, NMSS, TUG, Anxiety short form, Depression short form, Emotional and behavioral dyscontrol short form, Fatigue Severity Scale, Pain Intensity and Interference short form, MoCA, RBDSQ, QUIP-RS, C-SSRS, NPI, SCOPA-sleep, ISI, DBAS-16, Pittsburgh Sleep Quality Index, IRLS, OABSS, EQ-5D, PDQ-39, CGI, PGI, blood draw for safety labs (hematology, Complete Metabolic Profile and Liver Function Tests) and blood cannabis analysis, urinalysis, ECG, and urine pregnancy test are done. Study drug compliance check, adverse event check and blinding assessment are done. Participants will take their study drug upon their arrival to the clinic and record the taking time. Blood is drawn for cannabis testing and safety labs three hours after the dose. Participants will be monitored and vital signs and orthostatic blood pressures will be checked at one and three hours (2.5 mg/kg/day dose assessment visit) after taking the study drug. Home diary is collected and reviewed. Urine cups dispensed. In addition to the procedures above, for Visit 3 (3-4 days, 1.25 mg/kg/day), participants are told to bring in empty, partially used, and unused bottles of study drug at next clinical visit. Participants will be told not to take the study drug on the day of the next visit, as they will take it upon arrival under instruction by study staff. Participants are instructed to measure their tremors at home for three days prior to 2.5 mg/kg/day dose assessment visit. Participants will be given the questionnaires of SCOPA-sleep, Anxiety short form, Depression short form, Emotional and behavioral dyscontrol short form, EQ-5D-5L, C-SSRS. Study staff will call the participants on the 3rd to 5th day on 2.5 mg/kg/day to remind them to complete the questionnaires and bring it in at next clinic visit.

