Pre-dilution dosage unit: CBD Cannabis Extract (depending on the subject's weight it will contain either 3 or 4 gms CBD) Diluted Unit: CBD Cannabis Oral Solution (100mg/ml CBD)

The FDA has approved our IND. The DEA has approved the PI's amended DEA Schedule 1 license. Participants will be given bottles with 30/40 ml of study drug, at concentration of 100 mg/ml CBD or placebo and instructed how to take it. The study drug is best taken fasted, as food will increase Cmax and delay Tmax. The study drug could be taken with a small amount of food as needed if the participants experience nausea. The study drug will be taken orally, started at 1.25 mg/kg/day of CBD, once daily in the morning for four days, then increased to 2.5 mg/kg/day, twice daily at standard times, with a minimum of six hours apart (Figure 2 dosing plan). Participants are instructed to take it before breakfast (30 to 60 minutes) and the same before dinner. Participants are instructed not to drink grapefruit for seven days prior to the first dose of study medication and during the rest of the study.

The study drug is taken as normal on the mornings of assessments. As far as practical, the same assessor carries out assessments at each visit. Assessment data are stored and not made available at subsequent visits.

Figure 2: Dosing plan.

Legend: V: Visit. D: Day. QD: once a day. BID: twice a day. PC: Phone call.

V1: -28 to -1 day. Screening visit.

V2: Day 1, Baseline visit: The first day of CBD 1.25 mg/kg/day. 4 weeks within screening visit.

V3: Day 3/4, 1.25 mg/kg/day dose assessment visit: The third to fourth day of CBD 1.25 mg/kg/day. PC: Day 7-9, Questionnaire survey reminder phone call. The third to fifth day of CBD 2.5 mg/kg/day.

V4: Day 14, 2.5 mg/kg/day Dose Assessment Visit: The 10th day of CBD 2.5 mg/kg/day.

V5: Day 28, Safety follow up visit, 2 weeks after stopping study drug.

Participants take their routine anti-PD medication on the day of their clinical visit, and when ON (PD medications are working) the testing is done.

CBD and metabolite levels will be measurements: Blood CBD and metabolite levels will be measured at screening visit, each dose assessment visit, and safety follow up visit. Urinary CBD and metabolites levels will be tested at dose assessment visits and safety follow up visit. Potential drug-drug interactions:

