# 4. Liver function monitoring visit

Liver Function monitoring visit	Time	Note
Medical History	2	PRA
Concomitant Medications	2	PRA
Adverse Events (b) and drug abuse related AEs	3	PRA
Anxiety short form	2	Study subject
Depression short form	2	Study subject
Emotional and behavioral dyscontrol short form	2	Study subject
SCOPA-sleep	4	Study subject
EQ-5D	2	Study subject
C-SSRS	2	PRA
Vitals	5	PRA
Blood draw for liver function tests	10	CTRC
Total visiting time	36	0.5 hours

2.5 mg/kg/day Dose assessment visit	Time	Note
Vital Signs, orthostatic BP	10	PRA, Begore taking study drug
Taking study drug in clinic	2	Study subject
Cognitive assessment battery	60	PRA
Vital Signs, orthostatic BP	10	PRA, one hours after taking study drug
Medical History	2	PI, PRA
Concomitant Medications	2	PI, PRA
Adverse Events and drug abuse related AEs Withdrawal AEs and liver function related AEs	3	PI, PRA
Complete Physical Exam	10	PI
Neurological exam	10	PI
QUIP-RS	5	PI
CGI	1	PI
MDS-UPDRS (all 4 parts), H&Y, Schwab & England Activities of Daily Living Scale	30	PI, Study subject
Unified Dyskinesia Rating Scale (UDysRS)	5	PI, Study subject
MOCA	10	PRA
TUG	5	PRA
NMSS	10	PRA
Home diary collection and review	2	PRA
Tremor constancy and amplitude measure (k)	5	PRA, 2 hours after taking study drug
PSG equipment and data collected (u)	2	PRA
Blinding assessment	1	PRA
Study drug compliance check	2	PRA
C-SSRS	2	PRA
RBDSQ	2	PRA
NPI	5	
Anxiety short form	2	Study subject
Depression short form	2	Study subject
Emotional and behavioral dyscontrol short form	2	Study subject
SCOPA-sleep	5	Study subject
Insomnia Severity Index (ISI)	2	Study subject
Modified Dysfunctional Beliefs and Attitudes about Sleep Questionnaire (DBAS-16)	3	Study subject
Pittsburgh Sleep Quality Index	3	Study subject
IRLS	2	Study subject
Fatigue severity scale	3	Study subject

5. 2.5 mg/kg/day Dose assessment visit

Pain intensity and interference short form	2	Study subject
Bladder function-OABSS	3	Study subject
PDQ-39	5	Study subject
EQ-5D	2	Study subject
PGI-I	1	Study subject
PGI-C	1	Study subject
Urinalysis, pregnancy test if applicable	5	PRA
Urinary collected for CBD and metabolites levels test	2	PRA
Take picture of central face	5	PRA, Study subject
ECG (12-LEAD)	10	CTRC
Blood draw for Hematology, CMP, cannabis test	10	CTRC, 3 hours after taking study drug
Vital Signs, orthostatic BP	10	PRA, 3 hours after taking study drug
Total visiting time	275	4 hours

6.Safety follow up visit		
Safety follow up visit	Time	Note

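### As scheduled, the mid-dose C-SSRS is completed at home with no stated staff review before Visit 4 (5 to 11 days), while other sections describe a staffed visit that would close the gap

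*Combined protocol and SAP*

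**What the plan says.** **Home completion.** In Procedures at each visit, the Visit 3 text hands participants six forms: SCOPA-sleep, the anxiety and depression short forms, then "Emotional and behavioral dyscontrol short form, EQ-5D-5L, C-SSRS". Staff telephone on day 3 to 5 of 2.5 mg/kg/day "to remind them to complete the questionnaires and bring it in at next clinic visit". The Figure 2 legend in C.2 describes the contact in the same way: "PC: Day 7-9, Questionnaire survey reminder phone call". C.1 Study design counts five visits in total, and Appendix 1 shows a telephone call but no clinic visit between Visits 3 and 4.

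**Staffed visit.** Section IV.A, item 1.1, names a liver function monitoring visit separately from the dose assessment visits when it lists where abuse-related adverse events are collected. Assessment of tolerability of each dose level, in C.1, places a liver function test at a study visit on days 3 to 5 of every dose. Appendix 6, item 4, "Liver function monitoring visit", lists the same six instruments as the home packet, with vital signs, adverse-event collection and a blood draw. In that table the study subject completes five of the instruments and the PRA (study staff) does the C-SSRS.

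**Mid-dose repeats.** C.1 Study design calls for repeated measures on days 3 to 5 of each dose, in clinic or at home: "The assessments include the assessment of tolerability and symptoms of hepatotoxicity", followed by the five self-report forms. The C-SSRS is not in that list.

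**The concern.** Sections IV.A (item 1.4) and D (item 6) list the C-SSRS among the safety assessments. Its use as a safeguard depends on someone reading the answers while they can still be acted on. A site that follows the Visit 3 text, Figure 2 and Appendix 1 literally would have the participant record the answers at home, continue study drug, and hand the form over at Visit 4. The result would then describe a past state.

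The same time point carries the tolerability and hepatotoxicity-symptom assessment in C.1 Study design, yet the scheduled contact is described only as a questionnaire reminder. Appendix 1 marks the two calls after dosing ends as calls to collect adverse events and withdrawal signs. The on-treatment call has no such footnote. In the open-label study the calls did have that purpose: "During phone calls participants were monitored for AEs".

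With two arrangements in the current text, sites and monitors cannot tell which one is required.

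**Working it through.** No power or error-rate formula applies. The check is day arithmetic, followed by a comparison of sections.

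**Inputs**
- Lead-in: "started at 1.25 mg/kg/day of CBD (once a day) for four days" (Dose escalation strategy), with Day 1 as the first dosing day (Figure 2 legend).
- Full dose up to Visit 4: "2.5 mg/kg/day of CBD (twice a day) for 10 (+4) days" (Dose escalation strategy).
- Call on day 3 to 5 of full dose (Procedures at each visit).

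**Reproducing the plan's calendar**
- First full-dose day = 1 + 4 = Day 5.
- Days 3 and 5 of full dose = 5 + 2 and 5 + 4 = Days 7 and 9, as in Figure 2.
- Day 10 of full dose = 5 + 9 = Day 14, the nominal Visit 4. With the window, 14 + 4 = Day 18.

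**Time from completion to first stated review** (Visit 4 day minus completion day, with completion on the call day)

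| Completed | Visit 4 on Day 14 | Visit 4 on Day 18 |
|---|---|---|
| Day 7 | 14 − 7 = 7 days | 18 − 7 = 11 days |
| Day 9 | 14 − 9 = 5 days | 18 − 9 = 9 days |

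The range is 5 to 7 days at the nominal visit and 5 to 11 days over the whole window. Appendix 1 puts the call in its Day 9 column, which gives 5 to 9 days.

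**Interval between staff-administered C-SSRS assessments on this schedule**
- Visit 3 is on Day 3 or 4.
- Shortest: 14 − 4 = 10 days. Longest: 18 − 3 = 15 days.

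**The two arrangements compared**

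| Point | C.1 Study design, Procedures at each visit, Figure 2, Appendix 1 | IV.A item 1.1, tolerability text in C.1, Appendix 6 item 4 |
|---|---|---|
| Contact at about Days 7 to 9 | Reminder call | Liver function monitoring visit, or a study visit on days 3 to 5 of the dose |
| Who does the C-SSRS | Participant, at home | PRA, 2 minutes (Appendix 6) |
| First staff sight of answers | Visit 4 | Same day, if held then |

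The Appendix 6 visit is fully itemised: 2 + 2 + 3 + 2 + 2 + 2 + 4 + 2 + 2 + 5 + 10 = 36 minutes, which matches its printed total. Appendix 6 gives no study day for it. The Days 7 to 9 timing comes from the tolerability text in C.1.

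**The case against.** The strongest objection is that the gap may not exist. A reader of the Visit 3 text alone might infer that the home form is the only suicidality check in the middle of full-dose treatment, and that staff ask nothing about adverse events between Visits 3 and 4. The documents do not support either inference. Appendix 6 lists a staff-administered C-SSRS and adverse-event collection at the liver function visit, IV.A names that visit, and the tolerability text in C.1 supplies its timing. Nothing in the documents marks the visit as withdrawn. C.1 Study design also requires tolerability and hepatotoxicity symptoms to be assessed at this point. What is missing is who asks and how. The Adverse Events row of Appendix 1 is unreadable in the extracted text and proves nothing either way.

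There is other contact as well. Equipment for the home sleep recording is attached in clinic after at least seven days on full dose, and there are visit reminders and a home diary. A participant may volunteer symptoms, and the text does not forbid discussing answers on the call. However, no C-SSRS or review of the form is assigned to any of these contacts, and the diary is reviewed at visits.

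The 11-day figure is the extreme case. It needs completion on Day 7 and Visit 4 on Day 18. Later completion shortens the delay.

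The objection removes the absolute reading. The conflict remains, and so does the absence of any stated review under the home arrangement.

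**Conclusion.** The point stands as a conflict between sections with a conditional safety gap. On the schedule in C.1 Study design, Procedures at each visit, Figure 2 and Appendix 1, a listed safety instrument goes without stated staff review for 5 to 7 days at the nominal Visit 4, and for up to 11 days with the window. This assumes completion on the call day and no disclosure by another route. If the liver function monitoring visit is held on Days 7 to 9, the C-SSRS is done by staff that day and the gap disappears.

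The documents do not settle which arrangement is in force. Either answer requires an edit: if the visit exists, the schedule omits it and the home C-SSRS duplicates it; if it does not, the home form needs a timely reader. The documents do not show that any participant would be harmed, and the point does not depend on that. It should be fixed because the remedy is small.

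**What to change.** Reconcile IV.A item 1.1, C.1 (Study design, Assessment of tolerability of each dose level, Procedures at each visit), the Figure 2 legend, Appendix 1 and Appendix 6 item 4 on whether a staffed visit takes place on days 3 to 5 of full dose.

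- **If it does:** add it to C.1 Study design (including the visit count), Procedures at each visit, Figure 2 and Appendix 1, and remove the C-SSRS from the home packet.
- **If it does not:** remove it from the sections that mention it. Use the Day 7 to 9 call for staff to ask the C-SSRS and the tolerability and hepatotoxicity-symptom questions that C.1 Study design already requires. Pass the answers to the investigator the same day. The other five forms can stay at home.

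Management of a positive answer is for the investigator and is not proposed here.

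The cost of the second route is protocol wording, a call script and an estimated 5 to 10 extra minutes on a call already scheduled. As a rough check, Appendix 6 allots 2 minutes to the C-SSRS, 2 to adverse events and 3 to withdrawal and liver-related events at the 1.25 mg/kg/day visit: 2 + 2 + 3 = 7 minutes. The first route costs schedule wording, plus the 36-minute visit if sites are not already holding it.

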#### C.2 Study Drug: CBD:

The study drug is supplied by NIDA; see Appendix 4 for Certificate of Analysis (COA). The study drug (CBD) is provided in the form of a thick liquid and will be diluted into a 100 mg/ml formulation with sesame oil. This procedure will be done by the PharmDs ([name], [name], and [name] as a consultant) or PI, according to the protocol we develop with guidance from NIDA and the University of Mississippi researchers that produced the material. The placebo will be made by the study Pharm Ds from USP grade sesame oil and food coloring. Because the placebo may be slightly different in appearance or taste, two study modifications are being done to preserve the blind. First, the study drug will be put into brown opaque bottles and the only study personnel to see the actual study drug will be the unblinded PharmD and the blinded CTRC PA that instructs the subject on how to take study drug. Further, the study drug is administered in a closed, vented room in the CTRC that removes the odor of cannabis within four minutes. After the study drug is administered and the study drug bottle closed, the PA will stay with the subject in the closed room while it is being vented for at least 10 minutes. The study design of parallel groups is being used instead of the original crossover design that was planned.

ElSohy Laboratories, Incorporated (ELI) will perform the stability testing. The laboratory is registered with the FDA and the DEA (Manufacturing and Analytical), all the planned analytical

procedures are validated, and the lab has extensive experience with the drug substance (CBD extract) and with a very similar drug product to ours. Controls for both CBD and THC content are used. The stability testing will be done in real time.

The shelf life will be determined by the testing described below. The final drug product will be stored at room temperature, 25°C.

The microbial testing for the final drug product will be carried out according to UPS 61 (total aerobic microbial count and total combined yeast/mold count) and USP 62 (for salmonella and E. coli), and the specification and acceptance criteria will be the same as recommended in USP <111> (microbiological examination of non-sterile products: Acceptance Criteria for Pharmaceutical Preparations and Substances for Pharmaceutical Use for non-sterile, non-aqueous products with oral administration). This will be the same for the product and placebo. Microbial Specifications:

- Route of Administration: Nonaqueous preparations for oral use.
- Total Aerobic Microbial Count:<103 cfu/mL •
- Total Combined Yeasts/Molds Count: <102 cfu/mL
- Specified Microorganism(s): Absence of Escherichia coli (1 g or 1 mL)

The CBD extract will be shipped and stored frozen. The final drug product will be prepared within 24 hours of being given to the subject. Once prepared it will be kept at room temperature. The subject will take home the final drug product in 60 ml amber bottles and take it orally for up to 20 days. The stability study will be carried out only at room temperature at the following time points: 0, 1 week, 2 weeks, 3 weeks, 1 month, 2 months, and 3 months. Duplicate analyses will be performed at each time point. Microbial testing will be carried out at the 0 time point for both drug product and placebo and again at the end of one month to show that no change in bioburden occurred during the one month storage at room temperature.

Three manufacturing batches will be prepared (validation lots). These will be subjected to analysis to show consistency of the manufacturing process.

The analytical specification will be that the analytical value should be within 10% of the nominal concentration (i.e. 100 mg CBD/ml should analyze for 90-110 mg/ml). The analytical method is validated for Linearity, LOD, LOQ, accuracy and precision for both CBD and THC.

The specification for the drug product will be:

Appearance: Greenish-yellowish brown, oily solution

Potency: CBD Concentration = 100 mg/mL = 10% solution;  $\pm 10\%$  variation in measured potency (90 to 110 mg/mL) is allowed due to manufacturing and analytical variation. Other Cannabinoids:

- THC not greater than 5 mg/mL (0.5% solution)
- CBD:THC ratio not less than 20:1

We will provide the FDA with a final report with statistical analysis.

We will prepare oral solution of 100 mg/ml CBD (10% CBD) and 3.31 mg/ml THC (0.33% THC) in 60 ml capacity amber glass bottles.

Each bottle will have 30 or 40 mL depending on how much the subject weighs.

- 30 mL CBD Cannabis extract oral solution filled: Each bottle will have 5055 mg of extract placed in it (3000 mg CBD), filled to 30 mL mark with sesame oil.
- 40 mL CBD Cannabis extract oral solution filled: Each bottle will have 6740 mg of extract placed in it (4000 mg CBD), filled to 40 mL mark with sesame oil.

[figure not shown]
Dosage Form and Strength

Pre-dilution dosage unit: CBD Cannabis Extract (depending on the subject's weight it will contain either 3 or 4 gms CBD) Diluted Unit: CBD Cannabis Oral Solution (100mg/ml CBD)

The FDA has approved our IND. The DEA has approved the PI's amended DEA Schedule 1 license. Participants will be given bottles with 30/40 ml of study drug, at concentration of 100 mg/ml CBD or placebo and instructed how to take it. The study drug is best taken fasted, as food will increase Cmax and delay Tmax. The study drug could be taken with a small amount of food as needed if the participants experience nausea. The study drug will be taken orally, started at 1.25 mg/kg/day of CBD, once daily in the morning for four days, then increased to 2.5 mg/kg/day, twice daily at standard times, with a minimum of six hours apart (Figure 2 dosing plan). Participants are instructed to take it before breakfast (30 to 60 minutes) and the same before dinner. Participants are instructed not to drink grapefruit for seven days prior to the first dose of study medication and during the rest of the study.

The study drug is taken as normal on the mornings of assessments. As far as practical, the same assessor carries out assessments at each visit. Assessment data are stored and not made available at subsequent visits.

Figure 2: Dosing plan.

Legend: V: Visit. D: Day. QD: once a day. BID: twice a day. PC: Phone call.

V1: -28 to -1 day. Screening visit.

V2: Day 1, Baseline visit: The first day of CBD 1.25 mg/kg/day. 4 weeks within screening visit.

V3: Day 3/4, 1.25 mg/kg/day dose assessment visit: The third to fourth day of CBD 1.25 mg/kg/day. PC: Day 7-9, Questionnaire survey reminder phone call. The third to fifth day of CBD 2.5 mg/kg/day.

V4: Day 14, 2.5 mg/kg/day Dose Assessment Visit: The 10th day of CBD 2.5 mg/kg/day.

V5: Day 28, Safety follow up visit, 2 weeks after stopping study drug.

Participants take their routine anti-PD medication on the day of their clinical visit, and when ON (PD medications are working) the testing is done.

CBD and metabolite levels will be measurements: Blood CBD and metabolite levels will be measured at screening visit, each dose assessment visit, and safety follow up visit. Urinary CBD and metabolites levels will be tested at dose assessment visits and safety follow up visit. Potential drug-drug interactions:

The PI has worked with [name], to study possible drug interactions. CBD concentrations and adverse events will be monitored in the presence of concomitant medications which are inhibitors of CYP3A4 and 2C19.

There are many possible interactions, but some are more likely and clinically relevant. Thus, the PI will especially monitor for clinical symptoms that may be associated with these particular interactions. The following drugs may increase the level of CBD: fluoxetine, fluvoxamine, fluconazole, ticlopidine, and nefazodone. The following dugs may decrease the level of CBD:

carbamazine, phenytoin, phenobarbital, rifampin, and St. John's Wort. The following drugs may interact with CBD to cause their levels to increase: alprazolam, clonazepam, lorazepam, oxazepam, temazepam, zolpidem, clopidigrel, narcotics (codeine, methadone, oxycodone, hydromorphone, morphine), cyclosporine A, tacrolimus, propranolol, and acetaminophen. Participants will be instructed not to take more than 1 gram per day of acetaminophen.

CBD is a potent inhibitor of CYP2C19. The plasma level of clobazam, which is metabolized by CYP2C19, therefore is expected to increase if CBD is added. Clobazam, per Micromedix, causes somnolence (16-25%). In a recent study, Lancet Neurology 2016;15:270-278, using the a much higher dose of CBD study drug than as in our trial there was approximately twice as much somnolence AEs reported in participants on both CBD and clozabam than in participants on CBD and not clobazam. Thus clobazam will be exclusionary in this study.

The following is additional information relevant to the population of this study, Parkinson disease (PD).

CBD is metabolized by the hepatic CYP450 enzymes 2C19 and 3A4 and an inhibitor of these isoenzymes. Thus the expectation is that selegiline levels could increase. CBD may mildly induce the expression of 1A2, 2B6, and 3A4. Thus the expectation is that levels of rasagiline, ropinirole, and selegiline may decrease.

CBD is a relatively potent inhibitor of UGT1A9 and UGT2B7 and has no significant effect on other UGT isoenzymes. The expectation is that the level of rotigotine may increase.

CBD is highly protein bound, so rasagiline, selegiline, and rotigotine levels may increase transiently. Checking plasma concentration levels of these anti-PD medications is not a routine clinical practice. Thus the PI will monitor participants on these medications for clinical changes. The most important and likely adverse effects of a clinically significant increase in the level of selegiline is anxiety, dyskinesia, agitation, insomnia, and hallucinations. The most important and likely adverse effects of a clinically of rasagiline, ropinirole, and selegiline is an increase in the motor symptoms of Parkinson disease, which are resting tremor, bradykinesia, rigidity, and postural instability. The most important and likely adverse effects of a clinically significant increase in rotigotine is low blood pressure, somnolence, and impulse control disorders. Instructions to Participants at the End of Each Stage:

We will provide the following instructions about continued marijuana use at the end of the study to facilitate safety:

Cannabis (marijuana) is composed of many substances. Street cannabis is high in tetrahydrocannabinol (THC), which causes the "high" feeling. Street cannabis has lower concentrations of cannabidiol (CBD). The cannabis preparations sold at dispensaries have various concentrations of THC and CBD. The ratio of THC to CBD plays a role in a preparation's beneficial and adverse effects. Studies to date suggest that THC is especially risky in person with PD, because it may worsen thinking and coordination and cause psychiatric symptoms. The precise effects of all the substances in cannabis is unknown. Using marijuana should be under the supervision of your physician, with monitoring the symptoms of PD and other diseases, as well as the interactions of marijuana and other drugs you take.

